5.2 Additional study treatment

No additional study treatment will be given for the purpose of this trial.

6 Investigational product

6.1 Name and description of investigational product

Protamine Sulfate - a highly cationic peptide that binds to either heparin or low molecular weight heparin (LMWH) to form a stable ion pair, which does not have anticoagulant activity. Protamine is used to counteract the anticoagulant effect of heparin before surgery; after renal dialysis; after open-heart surgery; if excessive bleeding occurs and when an overdose has inadvertently been given. Protamine is registered in Australia (reg. number: AUST R 27971) and distributed by Sanofi Aventis Australia. The product is a sterile, pyrogen-free, clear, colourless 1% solution of Protamine Sulfate (Salmine) in Sodium Chloride Intravenous Infusion B.P. (0.9% w/v) adjusted to a pH of 2.5 to 3.5 and supplied in 5 mL glass ampoules.

6.2 Summary of findings from non-clinical and clinical studies

Protamine is a positively charged peptide consisting of approximately 32 amino acids, and neutralises the effect of heparin through electrostatic binding between the cationic arginine

groups of protamine and the anionic heparin in a 1:1 ratio. This creates a neutral protamineheparin salt aggregate, and the binding of protamine to heparin dissociates the antithrombin/heparin complex, leading to the recovery of the original anti-thrombin activity.^{13–16}

Protamine has a rapid onset of action: a heparin-neutralising effect within 5 min for unfractioned heparin, and a relatively short half-life of about 10 min in healthy volunteers.¹⁷ Clearance of low-molecular-weight heparin by protamine depends on the molecular weight of heparin, with small heparin fragments being more difficult to neutralise than larger molecules.¹⁸

Whilst protamine primarily neutralises heparin, protamine has anticoagulant properties that are attributed to an interaction with platelet function, interference with coagulation factors, and stimulation of clot breakdown. First, protamine reduces platelet activity and aggregation, but the underlying mechanism is multifactorial.^{19–21} Second, protamine may interfere with coagulation factors involved in clot formation, especially in the case of higher protamine doses. In vitro experiments showed that protamine mediates the down-regulation of thrombin generation, leading to a reduced conversion of fibrinogen to fibrin, reduces the rate of factor V activation by thrombin and factor Xa, and decreases factor VII activation by tissue factor thrombin activity.^{21–} ²⁴ Third, the decreased thrombin concentrations associated with protamine administration may also potentiate fibrinolysis.²⁵

6.3 Summary of know potential risks

Protamine administration is associated with immunological and inflammatory alterations, and may induce an anaphylactic response with hypotension, bradycardia, pulmonary vasoconstriction, and allergy, as the most frequently reported side-effects. A systematic review of prospective and retrospective studies reporting serious anaphylactic reactions caused by protamine administration revealed an incidence of adverse reactions varying from 0.19% to

0.69%.²⁶ Patient risk factors for an anaphylactic response include treatment of diabetes mellitus with protamine-containing insulin and allergies for fish proteins.²⁷

Infusion of protamine is frequently associated with a transient drop in blood pressure and a rise in pulmonary arterial pressure. Vascular reactivity to protamine is most likely mediated by increased mechanical stretch-induced intracellular endothelial calcium release, and nitric oxide production.^{28,29} This transient systemic hypotension and pulmonary hypertension reverses without treatment.

6.4 Description of justification of route of administration and dosage

A comprehensive review on dosing of protamine suggests that protamine administration based on the initial heparin dose should target a ratio below 1:1 in order to prevent protamine-related coagulopathy and bleeding, but the exact ratio is not elaborated and may vary between 0.6 and 1.0 based on the initial heparin dose.²¹

In this study the final dosage of protamine will be at the operator's discretion but should not exceed total heparin dose.

6.5 Preparation and labelling of investigational medicinal product

Two 10cc syringes, one with protamine (10mg/mL) and one placebo (10mL NaCl 0.9%) will be prepared by either the anaesthetics team or the nursing staff. Dependent on outcome of randomisation, one syringe will be labelled with 'A' and contains protamine, and the other will be labelled 'B' and contains placebo, or vice versa. This will be documented, and primary operators will be blinded to the true contents of syringe A and B. (See also 7.3)

7 Methods

7.1 Study parameters/endpoints

Primary and secondary endpoints are mentioned in paragraph 2.1 and 2.2, and full definitions will be described in chapter 13.

7.2 Randomisation, blinding and treatment allocation

Randomisation forms will be generated by computer-generated code, numbered, and sealed in opaque envelopes, that conceals the treatment designation. Stickers with 'A' and 'B' will also be provided in the envelope.

For patients randomised to protamine syringe A will contain 100mg (10mg/mL) protaminesulphate. Syringe B will contain 10mL 0.9% NaCl. For patients randomised to placebo, syringe A will contain 10mL 0.9% NaCl, and syringe B will contain 100mg (10mg/mL) protaminesulphate.

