4.4 Sample size

Sample size calculation for a 25% reduction of baseline 13 ± 10 min of TTH after sheath removal, with >80% power and a 2-sided a of 0.05 leads, and a drop-out of 15% to a minimum of 400 enrolled patients.

The baseline TTH is based on several published studies: a randomised trial comparing proglide and prostar devices after large-bore arteriotomy (mean TTH was 9.8±17 minutes after ProGlide and 13±19 minutes after ProStar)¹¹ and a prospective registry of the Manta device (mean TTH 2.4 minutes)¹².

5 Treatment of subjects

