7.3 Study procedures

The patient will be consented for the study prior to the TAVI procedure. After successful deployment of the THV, the patient will be randomised, as described in paragraph 7.2.

Prior to removal of the large sheath, ACT will be assessed. Then syringe A will be injected and sheath-removal/arteriotomy closure per operator's discretion will be performed. If haemostasis is achieved, time between sheath removal and confirmed arterial haemostasis will be recorded.

If after 10 minutes no haemostasis is achieved, syringe B may be injected per operator's request. This preserves the blinding of primary operators but ensures if ongoing bleeding issues that protamine is injected to improve haemostasis (as would in routine management). The need for syringe B will be documented on the study registration form. A sticker on arterial access-site dressing will be applied, with a notification if compression on the ward is required, so delayed haemostasis failure can be documented. Femoral ultrasound will be performed 3-48h afterwards

to assess haematoma size and vascular complications. Time to discharge will be documented. Any occurrence of secondary endpoints during in-hospital stay will be documented.

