9.2 Interim analysis

Interim analyses will be performed when 100 patients are enrolled in each arm of the study. (also see paragraph 8.5).

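### No stratification or blocking by site or planned closure device is specified, which costs modest precision on time to haemostasis

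*Protocol*

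**What the plan says.** Protocol 7.2 is the only account of how patients are allocated: "Randomisation forms will be generated by computer-generated code, numbered, and sealed in opaque envelopes". It goes on to describe the A and B stickers and the syringe contents. Neither 7.2 nor any other section mentions stratification, blocking or separate series for the three hospitals named in 4.1.

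Under 7.3 the patient is randomised after the valve is deployed. Then "Prior to removal of the large sheath, ACT will be assessed", syringe A is given, and "sheath-removal/arteriotomy closure per operator's discretion will be performed". The closure method is therefore carried out, and may be settled, after allocation.

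The sample size in 4.4 rests on TTH: "Sample size calculation for a 25% reduction of baseline 13 ± 10 min of TTH after sheath removal", with more than 80% power at two-sided 0.05 and "a drop-out of 15% to a minimum of 400 enrolled patients". As background, the same section cites mean TTH of 9.8 min (SD 17) for ProGlide and 13 min (SD 19) for ProStar, both from one randomised trial, and 2.4 min for the Manta plug, from a registry. The data lists in 7.4 do not name the closure device, though they are expressly not exhaustive.

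**The concern.** By the protocol's own citations, the plug-versus-suture difference in mean TTH is two to three times the effect the trial is sized to detect. If both types are used, device mix adds variance to TTH, and a chance difference in mix between arms adds noise to the treatment comparison. Much of this could be removed at almost no cost.

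The timing makes it a protocol matter. Strata and blocks must be fixed before envelopes are sealed. An analysis can adjust cleanly for planned device only if somebody writes it down before allocation. At stake is precision on TTH. The other primary outcome, procedural haemostasis failure, is not examined here.

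**Working it through.** **Inputs**
- Effect 0.25 × 13 = 3.25 min, SD 10, two-sided 0.05, 15% drop-out, at least 400 enrolled (4.4).
- 1:1 allocation is assumed from the interim wording in 9.2: "Interim analyses will be performed when 100 patients are enrolled in each arm of the study".
- Device gap 9.8 − 2.4 = 7.4 min, or 13 − 2.4 = 10.6 min (4.4).
- Plug share p: not in the protocol. Assumed 10% to 50%.

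**The plan's own figure**
- n per arm = 2(z₀.₉₇₅ + z_power)² × 10² / 3.25².
- At 80% power: 149 per arm, 298 in total, and 298/0.85 gives 351 enrolled.
- At 85% power: 171 per arm, 342 in total, and 342/0.85 gives 403 enrolled.
- In reverse, 400 × 0.85 = 340 evaluable, or 170 per arm, and power is 85.0%. The stated minimum of 400 is consistent with more than 80% power.

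**Variance due to device.** Between-device variance is p(1 − p) × gap². Taking the stated SD of 10 as the total SD (variance 100) and 170 per arm:

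| Gap (min) | p | Between-device variance | Share of 100 | Remaining SD | Power if adjusted | Enrolled for 85% power |
|---|---|---|---|---|---|---|
| 7.4 | 0.10 | 0.09 × 54.76 = 4.9 | 4.9% | 9.75 | 86.7% | 382 |
| 7.4 | 0.50 | 0.25 × 54.76 = 13.7 | 13.7% | 9.29 | 89.7% | 346 |
| 10.6 | 0.10 | 0.09 × 112.36 = 10.1 | 10.1% | 9.48 | 88.5% | 360 |
| 10.6 | 0.50 | 0.25 × 112.36 = 28.1 | 28.1% | 8.48 | 94.2% | 290 |

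The comparators are 85.0% power and 403 enrolled without adjustment. Because p(1 − p) peaks at 0.5, the 50% rows are upper limits.

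**Chance imbalance under unrestricted randomisation.** The SD of the between-arm difference in plug share is √(2p(1 − p)/170), which is 3.3 points at p = 0.10 and 5.4 points at p = 0.50. Multiplied by the gap, the TTH difference shifts with an SD of 0.24 to 0.57 min (95% within about ±0.5 to ±1.1 min), against 3.25 min.

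**Type I error.** Simulating an unadjusted t-test with no treatment effect, p = 0.50 and a 10.6 min gap (10,000 runs) gave 0.0496.

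**Sensitivity to the SD**
- If 10 is the within-device SD only, the total SD is √(100 + p(1 − p) × gap²), which is 10.4 to 11.3 for plug shares of 20–50%. Unadjusted power is then 82% down to 75%; adjustment brings it back to about 85%.
- Against the cited SDs, even at p = 0.50, device explains 13.7/19² = 3.8% to 28.1/17² = 9.7% of the variance.

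**The case against.** The strongest reply is that 7.2 states nothing false. A reader might infer that patients are drawn from one plain, unblocked list, but the text does not say so; it is silent, and site series or blocks are not ruled out. Most of the precision gain comes from adjustment, which may be in an SAP that is not shown, and stratifying without adjusting would not deliver it. This stands in large part. It does not dispose of the point, because allocation is what 7.2 sets out to fix, and no analysis plan can use a planned-device field that was never recorded.

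The device gap is also soft. The 2.4 min comes from a registry and the 9.8 and 13 min from a trial in aortic aneurysm repair (reference 11), so device is mixed up with procedure and population. Within that trial the two suture devices differ only 1.3-fold (13/9.8). No TTH by site is given. This stands, and it limits the size of the claim.

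Three further inferences are tempting and not supported:
- That chance imbalance biases the result or inflates the type I error. The imbalance is random, and the standard error already reflects it.
- That power is already short, so the loss is critical. On the stated inputs 400 enrolled gives 85%. Power is lower with SDs of 17–19, but device then matters least.
- That ACT is collected for no purpose. Its role in the analysis cannot be judged without the SAP.

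Finally, stratification has a price. Under 6.5 the anaesthetic or nursing staff label the syringes by allocation, so people in the room know past assignments. Small strata with fixed blocks would make later envelopes easier to guess. The remedy must deal with that.

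**Conclusion.** The point holds as a modest efficiency gain that is cheap to take. It shows no error in the stated sample size. The plausible benefit is about 2 to 9 percentage points of power, or roughly 20 to 115 fewer patients for the same 85% power (403 − 382 = 21; 403 − 290 = 113).

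Those figures assume that the stated SD of 10 is the total SD, that the cited plug–suture gap carries over to this trial, that plugs make up 10–50% of closures, and that TTH would otherwise be compared as unadjusted means. If the true SD is near 17–19, or few plugs are used, the benefit is towards or below the lower end. Stratification secures balance and obliges sites to record the planned device; adjustment yields most of the precision.

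**What to change.** - **Before the envelope is opened (7.3, 7.4):** record the planned closure device, plug or suture. The planned device is the right stratum because closure itself follows randomisation and syringe A.
- **Allocation (7.2):** supply separate envelope series by site and planned device, 3 × 2 = 6 series, with block sizes that vary at random and are concealed from site staff. Blocking also helps the two arms reach the 100 per arm interim trigger at about the same time.
- **Analysis (9.1 or the SAP):** adjust the TTH comparison for site, planned device and ACT taken before syringe A.
- **If enrolment has begun:** keep the existing list, record planned device from now on, and adjust only.

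The cost is a few more envelope series and one extra field. The small strata need varied block sizes to limit predictability. No extra patients are needed and clinical care does not change.

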7.3 Study procedures

The patient will be consented for the study prior to the TAVI procedure. After successful deployment of the THV, the patient will be randomised, as described in paragraph 7.2.

Prior to removal of the large sheath, ACT will be assessed. Then syringe A will be injected and sheath-removal/arteriotomy closure per operator's discretion will be performed. If haemostasis is achieved, time between sheath removal and confirmed arterial haemostasis will be recorded.

If after 10 minutes no haemostasis is achieved, syringe B may be injected per operator's request. This preserves the blinding of primary operators but ensures if ongoing bleeding issues that protamine is injected to improve haemostasis (as would in routine management). The need for syringe B will be documented on the study registration form. A sticker on arterial access-site dressing will be applied, with a notification if compression on the ward is required, so delayed haemostasis failure can be documented. Femoral ultrasound will be performed 3-48h afterwards

to assess haematoma size and vascular complications. Time to discharge will be documented. Any occurrence of secondary endpoints during in-hospital stay will be documented.

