Study protocol

Routine versus selective protamine administration to reduce bleeding in transcatheter aortic valve implantation (ACE-PROTAVI)

Melbourne, 10 March 2021

Protocol Synopsis

Title	Routine versus selective protamine administration to reduce bleeding in transcatheter aortic valve implantation
Acronym	ACE-PROTAVI
Principal	[name]
Investigators	[name]
J	The Heart Centre, The Alfred Hospital, Melbourne Australia
	Department of Cardiology, Epworth Healthcare, Melbourne Australia
Co-	[name]
investigators	[name]
	[name]
	[name]
	[name]
	[name]
Study	Routine administration of protamine reduces vascular and bleeding
Hypothesis	complications in TAVI patients, compared with selective administration,
	therefore improving clinical outcomes (reduced morbidity and mortality),
	but also reducing healthcare costs (by reducing length of stay, additional
 	vascular interventions, and improving post-procedural recovery).
Study Design	Randomised controlled trial in which patients are randomised between
	routine protamine administration at the end of the procedure, or selective
Ctudy	Use of protamine if clinical scenario requires it.
Sludy	Patients with symptomatic severe aonic stenosis of regulgitation who are
population	surgical risk, frailty, and other clinically relevant factors
Primary	Time to haemostasis: elansed time after sheath removal and first observed
obiective	and confirmed arterial haemostasis.
Secondary	- Composite rate of all-cause mortality, major and minor bleeding
objectives	and vascular complications according to VARC-2 criteria at 30-day
•	follow-up
	- Each individual component of first secondary endpoint.
	 Need for transfusion for (access-site related) bleeding
	 Hematoma size by vascular ultrasound
	- Myocardial infarction
	- Stroke
	- Length of stay
	- Rate of delayed haemostasis failure
Inclusion	Patients undergoing elective trans-temoral TAVI for severe aortic valve
	stenosis with any commercially available transcatheter heart valve.
EXCIUSION oritoria	- Documented protamine allergy or anaphylaxis
criteria	- Recent PUI (< 3 months)
	- Fianneu alterial access via surgical cut-down
Intervention	Routine protamine administration at the time of sheath removal after
	successful denloyment of THV

Table of contents

Protocol Synopsis	2
Table of contents	3
1 Introduction and rationale	6
1.1 Lay summary	6
1.2 Background	6
1.3 Study hypothesis and aims	7
1.4 Trial registration	8
2 Objectives	8
2.1 Primary objective	8

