2.1 Primary objective

The primary objectives of this study are to determine if routine protamine administration, compared with selective protamine administration, reduces the risk of procedural haemostasis failure and reduces the time to haemostasis (TTH): elapsed time after sheath removal and first observed and confirmed arterial haemostasis.

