9.1 Baseline characteristics, primary and secondary outcomes

Summary statistics, including mean and standard deviation or median and interquartile range, will be calculated for all baseline characteristics by treatment arm.

Outcome analysis will be based on the intention-to-treat principle. The intention-to-treat analysis will include all randomised subjects and all events during the time from randomisation to the trial termination. The trial termination will be fixed by the DSMB as described above.

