13.1 Primary outcome

The primary endpoint is described in chapter 2.1. Procedural haemostasis failure will be defined as failure to achieve haemostasis at the arteriotomy site leading to alternative treatment (e.g. fem-stop device, or adjunctive endovascular ballooning/stenting). Time to haemostasis will be measured in the time (minutes) elapsed after large sheath removal and first observed and confirmed arterial haemostasis.

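### Time to haemostasis is to be recorded only when haemostasis is achieved, so the protocol leaves procedural haemostasis failures without a defined value in the endpoint that drives the sample size

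*Protocol*

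**What the plan says.** Section 7.3 describes the sequence: syringe A, sheath removal and closure, then "If haemostasis is achieved, time between sheath removal and confirmed arterial haemostasis will be recorded". It goes on: "If after 10 minutes no haemostasis is achieved, syringe B may be injected per operator's request". For these patients the need for syringe B is documented. No clock time is asked for syringe B, for the start of any alternative treatment, or for final haemostasis, and the text does not say whether the TTH clock runs on.

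Section 13.1 puts two definitions side by side. For failure: "Procedural haemostasis failure will be defined as failure to achieve haemostasis at the arteriotomy site leading to alternative treatment", with a compression device, ballooning and stenting as examples. For TTH: "Time to haemostasis will be measured in the time (minutes) elapsed after large sheath removal and first observed and confirmed arterial haemostasis". The second definition carries no condition, and it gives no value or censoring rule for a failure.

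Section 2.1 makes procedural haemostasis failure and TTH joint primary objectives. The synopsis names TTH alone. The sample size in section 4.4 rests on TTH alone. Section 9.1 says: "The intention-to-treat analysis will include all randomised subjects".

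**The concern.** Whether a TTH value exists would depend on what happens after randomisation, and on the very event that section 2.1 expects protamine to reduce. If failures are mostly patients who would have taken a long time, leaving them out removes more long times from the arm with more failures. That arm then looks faster than it is. A true benefit of routine protamine on TTH would be understated. With no true effect on TTH, routine protamine would look slower.

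If instead a failure is timed to haemostasis after alternative treatment, TTH partly measures how quickly the operator changed course. The three sites could read the sentence differently.

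This is more than an analysis choice that can wait for a statistical analysis plan. A plan can choose how to handle failures, but it cannot recover a clock time that was never written down in the procedure room.

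**Working it through.** **1. The planned comparison.** Inputs from section 4.4: control mean 13 min, SD 10 min, 25% reduction, two-sided alpha 0.05, power above 80%, 15% drop-out, at least 400 enrolled. Equal allocation is assumed, because no ratio is stated and the interim analysis refers to 100 per arm.

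- Difference: 0.25 × 13 = 3.25 min.
- n per arm = 2(z₀.₉₇₅ + z_power)² × 10² / 3.25².
- At 80% power: 148.6, so 149 per arm and 298 in total; 298/0.85 gives 351 enrolled.
- At 85% power: 170.005, so 171 per arm and 342 in total; 342/0.85 gives 403 enrolled.
- Conversely, 400 × 0.85 = 340, or 170 per arm, has power 0.850.

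The stated 400 is therefore reproduced at about 85% power, with TTH as a mean over all evaluable patients.

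**2. The wording, side by side.** Section 7.3 records a time if haemostasis is achieved. Section 13.1 defines failure as haemostasis not achieved, leading to alternative treatment. Taken literally, the failures of 13.1 are the patients who do not meet the condition of 7.3. Having no haemostasis at 10 minutes is not the protocol's definition of failure; it only opens the way to syringe B.

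**3. Size of the bias if failures have no TTH.** The protocol gives no failure rates, so these are assumptions. Two pairs (selective v routine) are used: 10% v 5%, and 11.8% v 4.1%. The second pair is the bleeding and vascular complication rates (no protamine v routine protamine) of the observational study cited in section 1.2. They are stand-ins and not failure rates. Failures are taken to be exactly the longest times, which is the extreme case.

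For a lognormal time with mean m and log-scale SD σ, where σ² = ln(1 + (SD/m)²), the mean after dropping the longest fraction p is m × Φ(z₁₋ₚ − σ)/(1 − p).

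- Control (13, SD 10): σ² = ln(1.5917), σ = 0.682.
- Routine (9.75), SD scaled with the mean to 7.5: σ = 0.682.
- Routine (9.75), SD kept at 10: σ² = ln(2.0519), σ = 0.848.

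At 10% v 5%:

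- Control: 13 × Φ(1.282 − 0.682)/0.90 = 10.48.
- Routine, SD 7.5: 9.75 × Φ(1.645 − 0.682)/0.95 = 8.54; difference 1.94.
- Routine, SD 10: 9.75 × Φ(1.645 − 0.848)/0.95 = 8.08; difference 2.40.

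The same steps, with a gamma distribution computed numerically alongside, give these observed differences (selective minus routine, min):

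| Failures dropped | True difference | Routine SD 7.5 (gamma / lognormal) | Routine SD 10 (gamma / lognormal) |
|---|---|---|---|
| none | 3.25 | 3.25 / 3.25 | 3.25 / 3.25 |
| 10% v 5% | 3.25 | 1.90 / 1.94 | 2.37 / 2.40 |
| 11.8% v 4.1% | 3.25 | 1.44 / 1.52 | 1.86 / 1.94 |

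With no true effect (mean 13 and SD 10 in both arms) and 11.8% v 4.1% dropped, the observed difference is −1.49 (gamma) or −1.38 (lognormal): routine protamine looks slower.

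**4. Sensitivity to the assumptions.**

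- Failures drawn at random from times over 10 min, 11.8% v 4.1%: the difference falls from 3.25 to about 2.7 min, and with no true effect it is about −0.6 min. The direction is unchanged and the size smaller.
- Equal failure rates (5% or 10% in both arms): with SD 10 in both arms the difference stays at about 3.25-3.36 min. With the scaled SD it is about 2.6-2.9 min, but the 25% relative reduction is intact. With no true effect it is zero.

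**5. Power.** Dropping long times also cuts the SD. Starting from 170 per arm and SD 10 in both arms, power at 10% v 5% is 0.87 (gamma) or 0.97 (lognormal), against 0.85 with nobody dropped. At 11.8% v 4.1% it is 0.68 or 0.86.

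**The case against.** A reader might infer that failures are removed from the primary endpoint altogether. The documents do not support that. Sections 2.1 and 13.1 make procedural haemostasis failure a primary outcome in its own right, so each failure counts there, and a reduction in failures would show. Only the synopsis names TTH alone. The defect is confined to TTH.

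A reader might also infer that intention-to-treat is broken. That is not shown either. Section 9.1 includes all randomised subjects, no section excludes failures, and censoring, worst rank or a competing-event analysis could each keep them. The promise is put at risk but not withdrawn.

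The strongest objection concerns meaning. The sentence in 7.3 has no time limit, and section 7.1 sends the reader to chapter 13, where TTH is unconditional. A patient sealed after syringe B or after a balloon still reaches confirmed haemostasis, so few patients may lack a time. This reading is open, and step 3 of the working does not apply to it. It still needs a rule, because such a time mixes the effect of protamine with the timing of alternative treatment.

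The choice of estimator is commonly left to a statistical analysis plan, and its absence here is no finding. What remains is data capture, together with two sections that do not agree.

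**Conclusion.** The point holds as a conflict between 7.3 and 13.1, together with a capture rule that could leave TTH undefined, or dependent on the timing of alternative treatment, in procedural haemostasis failures. The direction of bias is firm provided that failure rates differ and failures tend to be long times: the arm with fewer failures is disadvantaged.

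The size is illustrative. Under extreme truncation the planned 3.25 min becomes about 1.9-2.4 min at 10% v 5%, and about 1.4-1.9 min at the stand-in rates of 11.8% v 4.1%. With no true effect, the stand-in rates make routine protamine look about 1.4-1.5 min slower. These figures rest on assumed failure rates, an assumed distribution, and the reading in which failures have no time.

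A reader might conclude that the trial would lose power. That does not follow in general, since power rises in some of these cases and falls in others. The harm is a biased estimate of the endpoint that sets the sample size. Because a missed time cannot be recovered later, the text should be settled before data are collected under it.

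**What to change.** In section 7.3, replace the conditional sentence with one that requires, for every randomised patient, the clock times of sheath removal, syringe B (if given), start of any alternative treatment, and final confirmed haemostasis.

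In section 13.1, state that patients with procedural haemostasis failure stay in the TTH analysis as not having achieved haemostasis without alternative treatment. They can take the worst rank in a rank-based comparison, or be a competing event in a cumulative-incidence analysis. They are not treated as missing. Say also whether the TTH clock continues after syringe B.

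Reconcile the synopsis, 2.1, 7.3 and 13.1, so that the primary outcome or outcomes and the TTH definition read the same throughout.

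The cost is a few more fields on the study form and a sentence or two in each of 7.3 and 13.1. A worst-rank or competing-event result is slightly harder to express in minutes. No clinical procedure has to change.
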